5 STUDY DESIGN

This is an open-label, multicenter, Phase 1b, dose-finding study of carfilzomib administered once-weekly in combination with lenalidomide and dexamethasone (KRd) in 28-day cycles to subjects with multiple myeloma.

Subjects may continue to receive study treatment for up to 18 cycles or until 1 or more of the following events occurs:

- Disease progression
- Allogeneic stem cell transplant
- Withdrawal from the study for any reason
- Study termination by the sponsor
- Death

Disease assessments will be conducted at Screening (within 21 days before dosing on Cycle 1 Day 1) and then on Day 1, \pm 3 days, of every cycle beginning with Cycle 2.

Response will be evaluated using the International Myeloma Working Group (IMWG) - Uniform Response Criteria (URC; [Rajkumar, 2011](#); [Appendix C](#)).

NDMM subjects may interrupt study treatment to proceed to hematopoietic stem cell collection, or stem cell collection and ASCT. The investigator will communicate transplant plans with the clinical study team. Upon completion of collection, subjects may resume study treatment (for up to the total of 18 cycles). Study treatment interruption for autologous hematopoietic stem cell collection may not exceed 42 days. Subjects with interruptions longer than 42 days may resume therapy on trial only with the written permission of the

sponsor study medical monitor. Subjects may interrupt study treatment and proceed to ASCT at any time after Cycle 4. Subjects who undergo ASCT may resume study treatment at any time up to posttransplant day 100, as elected by the investigator.

There will be 2 parts in the study.

The first part is the Dose-evaluation Component during which carfilzomib combination regimens will be evaluated ([Table 2](#) and [Figure 1](#)). Approximately 8 dose-limiting toxicity evaluable subjects will be enrolled into each opened Dose-evaluation cohort. Before opening Dose-expansion **arms**, it must be determined that there are not more than 2 dose-limiting toxicities in 8 DLT-evaluable subjects at the dose selected for Dose-expansion.

Dose-expansion **arms** may open once all safety data for at least 1 cycle at maximal dose carfilzomib is reviewed by the CSRC.

[figure not shown]
The second part is the Dose-expansion Component.

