5.7 ESTIMATED STUDY DURATION AND STUDY CLOSURE

The total study duration is expected to be a minimum of 60 months. Approximately 6 months will be required to enroll subjects in the RRMM Dose-evaluation Component of the study. Approximately 9 months will be required to enroll subjects in the RRMM Dose-expansion Component of the study. Subjects will be followed for up to 17 months in order to complete primary safety and efficacy evaluations with up to an additional 12 months of Active Follow-up.

It will take up to approximately **12** months to enroll NDMM subjects into Dose-evaluation Cohort 4, review the safety data, and enroll NDMM subjects into the NDMM Dose-expansion **Arm 3**. Subjects will be followed for up to 17 months on treatment (with an allowed interruption of up to 4.5 months for ASCT), and for 12 months for Active Follow up.

Based on these assumptions, it is estimated that the final analysis will occur approximately 60 months after the first subject is enrolled.

The end of study will occur when the last subject leaves Active Follow-up.

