For central laboratory FISH: Subjects with chromosomal abnormalities (CA) t (4;14) or t (14;16) in $\geq 10\%$ of screened plasma cells, and/or deletion 17p in $\geq 20\%$ of screened plasma cells are in high risk group. Subjects with other CA or normal cytogenetics are in standard risk group.

For local laboratory FISH (captured on eCRF): Subjects with chromosomal abnormalities (CA) t (4; 14) or t (14;16) and/or deletion 17p detected on FISH are in high risk group. Subjects with other CA or normal cytogenetics are in standard risk group.

Investigational Product (IP)

IP for this study refers to Kyprolis® (carfilzomib).

Informed Consent Date

The informed consent date is the date on which a subject signs the informed consent for this study.

International Staging System (ISS) Stage at Baseline

ISS stage at baseline will be calculated using serum beta-2 microglobulin and serum albumin value collected at baseline based on the criteria published by the International Myeloma Working Group ([Greipp 2005](#)).

ISS Stage I: Serum beta-2 microglobulin < 3.5 mg/L and serum albumin ≥ 3.5 g/dL

ISS Stage II: Serum beta-2 microglobulin < 3.5 mg/L and serum albumin < 3.5 g/dL or serum beta-2 microglobulin $3.5- < 5.5$ mg/L irrespective of the serum albumin

ISS Stage III: Serum beta-2 microglobulin ≥ 5.5 mg/L

Revised International Staging System (R-ISS) Stage at Baseline

R-ISS stage at baseline will be calculated using ISS (serum beta-2 microglobulin and serum albumin value collected at baseline, with ISS calculated as above), cytogenetic

risk group by FISH (central lab data, local lab data), and LDH, based on the criteria published by the International Myeloma Working Group ([Palumbo, 2015](#)):

R-ISS Stage I: Serum beta-2 microglobulin < 3.5 mg/L, serum albumin \geq 3.5 g/dL and standard risk CA by FISH and normal LDH

R-ISS Stage II: Not R-ISS I or III

R-ISS Stage III: ISS III and either high risk CA by FISH or greater than normal LDH

Last Dose Date

The last dose date is the date on which a subject is administered the final dose of any study drug.

Refractory to prior multiple myeloma therapy

Subject is refractory to a drug received in prior regimens if the data collected on prior multiple myeloma therapy CRF indicates that any of the following criteria is met:

- a. Best Response to any regimen containing the drug is stable disease or progressive disease
- b. Reason the drug was stopped is progression in any regimen

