- c. Date of relapse/progression is after start date and within 60 days after stop date of the drug in any regimen

Study Day 1

Study day 1 is the earliest date when carfilzomib, lenalidomide, or dexamethasone is given for subjects who receive at least one dose of study drug, enrollment date for subjects who are enrolled but not treated.

Study Day

The number of days from the study day 1 to a date of interest, inclusive: Study day = (date of interest – date of study day 1) + 1.

Unless otherwise specified, the timing of all study-related events, assessments, and interventions will be calculated relative to study day 1. Study day –1 will be the day before study day 1, and in general for assessments prior to study day 1, study day is defined as:

$$\text{Study Day } n = (\text{date of interest} - \text{date of Study day 1})$$

Subject Incidence Rate

The subject incidence rate for a given event is defined as the number of subjects with one or more reported occurrence of the event divided by the number of subjects who had the opportunity to experience the event.

Treatment-emergent Adverse Event

Treatment-emergent adverse events are **defined as any adverse events starting on or after the first dose of any study drug, and up to including 30 days after the last dose of any study drug or End of Study date, whichever is earlier.**

6. Analysis Sets

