9.6.1 Adverse Events and Disease-related Events

The Medical Dictionary for Regulatory Activities (MedDRA) version 21.0 or later will be used to code all adverse events (AEs) to a system organ class (SOC) and a preferred term (PT). The severity of AEs will be coded according to NCI-CTCAE v 4.03.

Treatment emergent adverse events will be summarized based on the number (%) of subjects experiencing events by MedDRA SOC and PT. The denominator for the percentage will be based on the number of subjects in the Safety Analysis Set.

Summaries of the subject incidence of the following TEAEs will be provided by SOC and/ or PT:

- All TEAEs
- TEAEs grade 3 or higher
- Fatal TEAEs
- Serious TEAEs
- TEAEs leading to withdrawal of carfilzomib
- Treatment-related TEAEs
- Treatment-related TEAEs grade 3 or higher
- **Treatment-related fatal TEAEs**
- **Treatment-related serious TEAEs**
- **Treatment-related TEAEs leading to withdrawal of carfilzomib**

Summaries that are displayed by SOC and PTs will be ordered by descending order of incidence of SOC and PT within each SOC for the total group. Summaries of TEAEs, and SAEs will be tabulated by SOC, PT and grade. Summaries of TEAEs, treatment-related AEs, and SAEs will also be provided by descending order of incidence of PTs in the total group

All TEAEs will be included in listings by subject. Listings of AEs determined to be DLTs, SAEs, AEs leading to discontinuation of study and AEs leading to discontinuation of investigational product will be provided.

A summary of the number of deaths and the cause of death, classified by deaths within 30 days of last dose of study drug and deaths more than 30 days after the last dose, will be provided.

Subject incidence of adverse events of interest (standardized MedDRA queries (**SMQ**) and/or Amgen MedDRA queries (**AMQ**)) will also be summarized according to their categories, PTs and grade. The adverse events of interest would include

- Acute renal failure (SMQ Narrow search)
- Cardiac arrhythmias (SMQ Narrow search)
- Cardiac failure (SMQ Narrow search)
- **Cardiomyopathy (SMQ Narrow search)**

- Dyspnoeas (HLT) - MedDRA Search Strategy HLT
- Embolic and thrombotic events, venous (SMQ Narrow search)
- Haematopoietic erythropenia (SMQ Broad search)
- Haematopoietic leukopenia (SMQ Narrow search)
- Haematopoietic thrombocytopenia (SMQ Narrow search)
- Haemorrhage terms (excl laboratory terms) (SMQ Narrow search)

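### For newly diagnosed subjects who resume KRd after on-study ASCT, transplant-gap AEs count as treatment-emergent and post-ASCT responses probably count toward CRR; no planned summary separates either

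*SAP*

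**What the plan says.** **Transplant on study.** Protocol section 5, on NDMM subjects: "Subjects may interrupt study treatment and proceed to ASCT at any time after Cycle 4". On return: "Subjects who undergo ASCT may resume study treatment at any time up to posttransplant day 100, as elected by the investigator". Protocol section 5.7 plans for treatment "with an allowed interruption of up to 4.5 months for ASCT".

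**AE window.** SAP section 5 sets the window as "starting on or after the first dose of any study drug, and up to including 30 days after the last dose" (whichever drug that is), stopping at End of Study if that comes first. The closing date is defined in the same section: "The last dose date is the date on which a subject is administered the final dose of any study drug". Protocol 12.2.1.1 collects AEs from consent to 30 days after the last dose and does not suspend collection for ASCT. In SAP 9.6.1, "Summaries of the subject incidence of the following TEAEs will be provided by SOC" and/or preferred term, and the list includes all, Grade 3 or higher, fatal and serious events. It adds: "Subject incidence of adverse events of interest".

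**Response.** SAP section 5 takes the investigator's best confirmed response up to the analysis trigger date. SAP 9.5.1 builds ORR and CRR on it. Neither names ASCT as a cut-off.

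**Where ASCT appears in planned outputs.** SAP 9.2 counts subjects with stem cell collection or transplant. SAP 9.6.7 gives cycles received before transplant, and cycles in subjects without transplant. SAP 4.2 plans no subgroup analyses.

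**The concern.** The primary endpoint is the type, incidence and severity of AEs on once-weekly KRd, and clinical activity in NDMM is a secondary objective. A subject who has a transplant in mid-course and returns to KRd contributes events from the transplant interval to the KRd tables, and possibly a response reached only after transplant to the KRd CRR. Whether such an event counts as treatment-emergent depends on a later decision to resume, not on the event itself.

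The summaries would therefore show AE incidence and CRR for KRd with or without transplant, in a proportion that they do not display. CRR is the response measure most exposed. The two newly diagnosed KRd studies in Protocol Table 1 report a PR-or-better rate or ORR of 98%, which leaves ORR little room to rise.

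**Working it through.** **1. The plan's own figure.** The plan gives no figure on this point. Its one safety precision figure (Protocol 13.7, SAP 3.2) reproduces: 1 − 0.95^38 = 0.858, against a stated 86%. It is not in dispute.

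**2. AE trace.**
- *Subject who resumes:* the last dose is a post-ASCT dose. The window runs unbroken from first dose to 30 days after that dose, so every AE starting in the gap is a TEAE.
- *Subject who does not resume:* the last dose is the last pre-ASCT dose. An AE starting more than 30 days later is not a TEAE.
- *Both:* an AE starting within 30 days of the last pre-ASCT dose is a TEAE, even if it belongs to collection, conditioning or early transplant.

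**3. Length of the difference.** Gap: 4.5 × 30.4 = 136.8 days (30.4 days per month is the SAP's conversion). Less 30: 106.8 days at most per resuming subject.

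To put this in proportion, assume that ASCT follows Cycle 4 and that the gap runs from Cycle 4 Day 22 (day 3 × 28 + 22 = 106):
- 18 cycles completed: 106 + 136.8 + (13 × 28 + 21 = 385) + 30 = 657.8 days; 106.8/657.8 = 16%.
- 8 cycles completed: 106 + 136.8 + (3 × 28 + 22 = 106) + 30 = 378.8 days; 106.8/378.8 = 28%.

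**4. Response texts side by side.**
- Protocol 10.1.5: the two consecutive assessments must precede new therapy, explained there as off-protocol therapy.
- Protocol Appendix C: they must precede any new therapy, with no such explanation.
- SAP section 5: as Appendix C.
- SAP 9.5.2: the text censors PFS at non-protocol systemic treatment; the matching Table 4 row says only new anticancer therapy.
- SAP section 10: declares no change from the protocol analyses.

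ASCT is permitted on protocol, so under Protocol 10.1.5 it is not new therapy and later responses count. That is the likelier reading. It is not certain, because two of the texts omit the qualifier and neither document says how ASCT or its conditioning is classed.

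**5. What one subject is worth** (group sizes from SAP 9.1).
- Arm 3: 1/33 = 3.0 points.
- Arm 1 plus Cohort 4: 1/18 = 5.6 points.
- Arm 1 or Cohort 4 alone: 1/9 = 11.1 points.

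The number affected is not given. Assumed counts of 0, 1, 3 and 6 in Arm 3 give 0, 3.0, 9.1 and 18.2 points. For comparison, the exact 95% interval is 25.5–60.8% at 14/33, 33.5–69.2% at 17/33 and 42.1–77.1% at 20/33, a half-width of 17.5 to 17.8 points.

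Incidence counts a subject once, so an AE rate moves only if the subject had no such event outside the gap.

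**6. ORR against CRR.** Using the 98% only as a scale (those studies dosed twice weekly), the room left for ORR is 0.02 × 33 = 0.7 of a subject.

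**The case against.** The strongest reply is that little is hidden. Protocol 13.5.1 lists response data, PFS and DOR for all subjects, and SAP 9.6.1 lists all TEAEs by subject. With transplant dates at hand, a reader could trace events before and after ASCT in groups of 9, 9 and 33. This stands: what is missing is a tabulation, not the data. A reader might infer that the report offers no way to see the effect, and the documents do not support that.

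Second, the AE effect is conservative. The gap can only add events, AEs are all-cause by definition, and five treatment-related summaries rest on the investigator's causality assessment. This also stands in part, but the all-cause tables are not filtered by causality.

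Third, neither a split of AEs nor a pre-ASCT response rate isolates the effect of KRd. Transplant events can start within 30 days of the last dose, late KRd toxicity can appear in the gap, and a response after ASCT may owe something to further KRd cycles. A pre-ASCT rate also cuts transplanted subjects off after possibly only 4 cycles. All of this is correct. It governs how the extra tables are labelled; it does not make them uninformative.

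Fourth, it is tempting to state that post-ASCT responses do count toward CRR. The wording conflict makes that a likely reading only.

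**Conclusion.** The AE part follows directly from the SAP's definitions. The response part holds on the likelier reading, and the texts must be reconciled. The size is unknown and may be zero: ASCT is optional, transplant-ineligible subjects are enrolled, and no resumption rate is given. One to three affected subjects in Arm 3 would move a rate by 3.0 to 9.1 points, inside the interval half-width; six would match it. Those counts are assumptions.

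Three stronger inferences are not supported:
- *DLT assessment or dose selection is contaminated.* DLTs are assessed in Cycle 1, or Cycles 1 and 2 for Cohort 4 (Protocol 5.2), and ASCT comes only after Cycle 4.
- *Fatal TEAEs are inflated.* A subject who dies in the gap cannot resume, so in practice the longer window adds none.
- *The gap creates missed visits and hence PFS censoring.* Disease assessments fall on Day 1 "of every cycle beginning with Cycle 2", so a paused cycle schedules none. PFS and DOR need consistent wording only.

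The SAP plans no hypothesis test (section 2.2). The issue is how the descriptive NDMM tables read. The additions are a cheap improvement, not the repair of an invalid analysis.

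**What to change.** Keep the TEAE definition and all headline analyses.

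1. **SAP 9.5.1, NDMM:** add best confirmed response before ASCT (CRR, with ORR for completeness) beside the any-time rate. Use all treated NDMM subjects as denominator. Label it as truncated at ASCT, possibly after only 4 cycles, and not as a KRd-only effect.
2. **SAP 9.6.1, NDMM:** add one supportive table of TEAEs (Grade 3 or higher, serious, events of interest) by onset period: before ASCT; from ASCT (or start of conditioning, if recorded) to the first post-ASCT dose; after resumption. For subjects who do not resume, the middle period ends with their TEAE window. Note that late KRd toxicity may fall in the middle period. Cutting at transplant, and not at 30 days after the last pre-ASCT dose, keeps early transplant events out of the first period.
3. **Wording:** carry the off-protocol qualifier of Protocol 10.1.5 into Protocol Appendix C, SAP section 5 and SAP Table 4, and state whether protocol-permitted ASCT counts as new therapy.

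The cost is a few sentences and two or three descriptive tables, from dosing and transplant data already needed for SAP 9.2 and 9.6.7. The downside is a supportive CRR that will probably be lower than the headline, partly because pre-ASCT exposure is short; the label must say so.

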6.1 Safety Analysis Set

The safety analysis set includes all subjects who received at least one dose of study drug.

6.2 Response-Evaluable Analysis Set

The response-evaluable analysis set is defined as subjects who are included in the safety analysis set, have a baseline disease assessment and at least 1 post-baseline disease assessment, or dropped out due to AE prior to the first post-baseline disease assessment.

6.3 Pharmacokinetic Analysis Set

The pharmacokinetic analysis subset includes subjects in the safety analysis set that have sufficient carfilzomib exposure and plasma concentration versus time data for the estimation of PK parameters by a non-compartmental analysis on Day 8 of Cycle 1.

6.4 Pharmacodynamic Analyses Set

The pharmacodynamic analysis subset includes subjects in the safety analysis set that have at least one measurable PDn endpoints. Proteasome activity for the chymotrypsin-like, trypsin-like and caspase-like activities from whole blood will be reported for the collected time points to determine if carfilzomib treatment produces a pharmacodynamic reduction in proteasome activity relative to baseline activity levels.

7. Planned Analyses

7.1 Interim Analysis and Early Stopping Guidelines

A Cohort Safety Review Committee (CSRC) comprised of the lead investigator, selected additional investigators, the sponsor's study medical monitor, and sponsor's drug safety representative will review all available safety data and make recommendations regarding ongoing enrollment and opening of subsequent cohorts during the Dose Evaluation Component. The CSRC will also select the KRD regimens to be evaluated in the Dose-expansion Component.

No formal interim analyses with the purpose of stopping the study early for efficacy or futility will be conducted for this study.

7.2 Primary Analysis

No primary analysis is planned for this study.

7.3 Final Analysis

The final analysis will occur when last subject completes the last assessment in the study (last subject last visit).

Approximately 6 months will be required to enroll subjects in the RRMM Dose evaluation component of the study. Approximately 9 months will be required to enroll subjects in the RRMM dose-expansion component of the study. Subjects will be followed for up to 17 months in order to complete primary safety and efficacy evaluation with up to an additional 12 months of Active follow-up.

It will take up to approximately 12 months to enroll NDMM subjects into Dose-evaluation Cohort 4, review the safety data, and enroll NDMM subjects into the NDMM Dose-expansion Arm 3. Subjects will be followed for up to 17 months on treatment (with an allowed interruption of up to 4.5 months for ASCT), and for up 12 months for Active Follow-up.

Based on the assumption, it is estimated that the final analysis will occur approximately 60 months after the first subject is enrolled.

In preparation for this analysis, data will be subject to ongoing checks for integrity, completeness and accuracy in accordance with the Data Management Plan with the expectation that all outstanding data issues are resolved ahead of the snapshot. The data will be locked to prevent further changes, and a snapshot of the locked database will be used in the analysis.

8. Data Screening and Acceptance

8.1 General Principles

The objective of the data screening is to assess the quantity, quality, and statistical characteristics of the data relative to the requirements of the planned analyses. The database will be subject to edit checks outlined in the data management plan (DMP) by Amgen Clinical Data Management (CDM) department. Data inconsistencies and suspicious values will be reviewed and resolved before the database is locked.

8.2 Data Handling and Electronic Transfer of Data

The Amgen Global Study Operations-Data Management (GSO-DM) department will provide all data to be used in the planned analyses. This study will use the RAVE database. PK, FISH, MRD and biomarker data will be evaluated by central laboratory transferred to Amgen GSO-DM. The data handling and electronic transfer of data are described in the DMP.

8.3 Handling of Missing and Incomplete Data

Missing and incomplete data will be identified through programmatic checks and a review of the tables and listings created within Biostatistics. Missing and incomplete data will be identified for investigation, and possible resolution, by DM and Global Study Management prior to each planned data snapshot and final database lock.

The handling of dropouts and missing disease status assessments for the efficacy variables is described in the description of the analyses. In general, data will be analyzed as retrieved from the study database and no imputation for missing data will be performed. Exceptions to this rule are detailed as below.

Missing or incomplete dates for adverse events, concomitant medications will be imputed as outlined by the algorithms below.

Table 3. Imputation Rules for Partial or Missing Start Dates

Start Date		Stop Date						
		Complete: yyyyymmdd		Partial: yyyyymm		Partial: yyyy		Missing
		< 1 st dose	≥ 1 st dose	< 1 st dose yyyymm	≥ 1 st dose yyyymm	< 1 st dose yyyy	≥ 1 st dose yyyy	
Partial: yyyymm	= 1 st dose yyyymm	2	1	2	1	n/a	1	1
	≠ 1 st dose yyyymm		2		2	2	2	2
Partial: yyyy	= 1 st dose yyyy	3	1	3	1	n/a	1	1
	≠ 1 st dose yyyy		3		3	3	3	3
Missing		4	1	4	1	4	1	1

1 = Impute the date of first dose

2 = Impute the first of the month

3 = Impute January 1st of the year

4 = Impute January 1st of the stop year

Note: If the start date imputation leads to a start date that is after the stop date, then do not impute the start date.

Imputation Rules for Partial or Missing Stop Dates

1. Initial imputation
 - If the month and year are present, impute the last day of that month
 - If only the year is present, impute December 31 of that year
 - If the stop date is entirely missing, assume the event or medication is ongoing
2. If the stop date imputation leads to a stop date that is after the death date, then impute the stop date as the death date.
3. If the stop date imputation leads to a stop date that is before the start date, then there is a data error and do not impute the stop date. (ie, set the stop date as missing).

If a partial or complete stop date is present and the 'ongoing' or 'continuing' box is checked, then it will be assumed that the adverse event or concomitant medication is ongoing. Missing stop dates will not be imputed beyond the subject last contact date or data cutoff date.

Imputation Rules for Partial or Missing Death Dates:

1. If death year and month are available but day is missing:
 - If mmYYYY for last contact date = mmYYYY for death date, set death date to the day after the last contact date.
 - If mmYYYY for last contact date < mmYYYY for death date, set death date to the first day of the death month.
 - If mmYYYY for last contact date > mmYYYY for death date, data error and do not impute.
2. If both month and day are missing for death date or a death date is totally missing, do not impute.

The imputed death date will be used in calculation of duration of response, progression-free survival.

Imputation Rules for date of initial diagnosis:

If the day is missing and month and year < month and year of enrollment then impute 15 for the day.

If the day is missing and month and year = month and year of enrollment then impute day with 15 unless the day of enrollment is <15 then impute date of enrollment.

If the day and month are missing and year is < year of enrollment then impute July 1st.

If the day and month are missing and year = year of enrollment then impute July 1st unless the day of enrollment is <July 1st then impute January 1st.

